# of Heel Raises: (to be used only for plantarflexion scoring) Score 0 = 4 to 5 heel raises Score 1 = 2 to 3 heel raises Score 2 = Sufficiently plantar flexes to clear heel Score 3 = Plantar flexes ankle through range (gravity eliminated) Score 4 = trace or no muscle contraction NE = Non-evaluable						
0 = Holds test position against gravity with maximum resistance (gr.5) 1 = Holds test position against gravity with moderate resistance (but breaks with maximal resistance) (gr.4) 2 = Holds test position against gravity with minimal resistance (gr. 3+), or holds test position against gravity (gr.3) 3 = Able to partially complete ROM against gravity (gr.3-/2+), or able to move through ROM gravity eliminated (gr.2), or through partial ROM gravity eliminated (gr.2-) 4 = Trace (gr.1) or no muscle contraction (gr.0) NE = Non-evaluable						

2013-02-25

15 APPENDIX 3: ABBREVIATIONS

AAV2	Adeno-associated virus vector, serotype 2
AAV5	Adeno-associated virus vector, serotype 5
████	████████████████████
AAV8	Adeno-associated virus vector, serotype 8
AAVhu37	Adeno-associated virus vector, serotype hu37
AAVrh10	Adeno-associated virus vector, rhesus serotype 10
████ ████	████████████████████
████ ████	████████████████████
ABR	Annualized bleeding rate
AE	Adverse event
AESI	Adverse event of special interest
AFU	Annualized factor usage
AIDS	Acquired immunodeficiency syndrome
ALP	Alkaline phosphatase
ALT	Alanine aminotransferase
ANC	Absolute neutrophil count
Anti-HBc	Total Hepatitis B core antibody
APRI	AST-to-Platelet Ratio Index
aPTT	Activated partial thromboplastin time
ARDS	Acute Respiratory Distress Syndrome
AST	Aspartate aminotransferase
████	████████████████
████ ████	████████████████████
BID	Twice daily
BMI	Body mass index
████	████████████████████ ████████████████████
bp	Base pair
BP	Blood pressure
BU	Bethesda units

BUN	Blood urea nitrogen
BQL	Below Quantifiable Limits
°C	Celsius
CD4	Cluster of differentiation 4
CD8	Cluster of differentiation 8
CDC	U.S. Centers for Disease Control and Prevention
cDNA	Complimentary deoxyribonucleic acid
CIOMS	Council for International Organizations of Medical Sciences
Cl	Chlorine
CL	Central laboratory
C _{max}	Maximum drug concentration
CNS	Central nervous system
COVID-19	Coronavirus disease caused by SARS-CoV-2
CRP	C-reactive protein
CQA	Clinical Quality Assurance
CTA	Clinical trial agreement
CTCAE	Common Terminology Criteria for Adverse Events
CTL	Cytotoxic T lymphocyte
DMC	Data Monitoring Committee
DNA	Deoxyribonucleic acid
EASL	European Association for the Study of the Liver
EC	Empty capsid
ECG	Electrocardiogram
CRF/eCRF	Case report form/electronic case report form
ED	Exposure day
EDC	Electronic Data Capture
EHL	Extended half-life
ELISpot	Enzyme-linked immunospot assay
EOS	End of study
EQ-5D-5L	Euro quality-of-life five dimensions questionnaire
FAS	Full analysis set
FDA	U.S. Food and Drug Administration

IgG	Immunoglobulin G
IgG4	Immunoglobulin G subclass 4
IgM	Immunoglobulin M
IL	Interleukin
ILI	Influenza like illness
IND	Investigational new drug application
IRB	Institutional Review Board
ITR	Inverted terminal repeats
IU	International units
IV	Intravenous
LDH	Lactate dehydrogenase
LDL	Low-density lipoprotein
LFT	Liver function test
LL	Local laboratory
LPLD	Lipoprotein lipase deficiency
LPLV	Last Participant's Last Visit
LSEC	Liver sinusoidal endothelial cells
LTFU	Long-term follow-up
MERS-CoV	Middle East respiratory syndrome-related coronavirus
MHC	Major histocompatibility complex
████	████████████████████
mRNA	Messenger ribonucleic acid
NAb	Neutralizing antibody
NAAT	Nucleic acid amplification testing
NCT	National Clinical Trial
NHF-MASAC	National Hemophilia Foundation's Medical and Scientific Advisory Council
NHP	Non-human primate
PBMC	Peripheral blood mononuclear cells
PCR	Polymerase chain reaction
PHI	Protected health information
PI	Principal Investigator

PK	Pharmacokinetics
PML	Progressive multifocal leukoencephalopathy
PV	Pharmacovigilance
QoL	Quality of life
rAAV	Recombinant adeno-associated viral vectors
RBC	Red blood cells
rFVIII	Recombinant factor VIII
RNA	Ribonucleic acid
RPE65	Retinal pigment epithelium 65 gene
SAE	Serious adverse event
SAP	Statistical Analysis Plan
SARS-CoV-2	Severe acute respiratory syndrome coronavirus 2
SD	Standard deviation
SPK-8016	Study drug in this protocol ██ ██
SPK-9001	██ ██ ██
SUSAR	Suspected Unexpected Serious Adverse Reactions
TB	Tuberculosis
████	██
TEE	Thrombotic and/or embolic events
TNF α	Tumor Necrosis Factor alpha
TPMT	Thiopurine methyltransferase
TTR	Transthyretin
TTRm	Modified transthyretin
ULN	Upper limit of normal
URTI	upper respiratory tract infection
vg	Vector genome
VLDL	Very low-density lipoprotein
VWF	von Willebrand factor
WBC	White blood cell

WFH	World Federation of Hemophilia
WHO	World Health Organization
XLMTM	X-linked myotubular myopathy

16 APPENDIX 4: SUMMARY OF CHANGES FROM THE PREVIOUS PROTOCOL VERSION

AMENDMENT 2 SECTION	SUMMARY OF REVISIONS MADE	RATIONALE
1.1 Protocol Synopsis	Protocol Synopsis has been updated.	Updates reflect changes made throughout Amendment 2.
Study Schema Figure	Updated Study Schema Figure 1.	The study schematic was updated to include the two cohorts.
Schedule of Assessments	Updated Schedule of Assessments Table 1.	Additional screening and follow up is required. This includes screening labs, three to seven days prior to vector, Day -2 infusion of [REDACTED] and weekly follow up while on immunomodulation. In addition, the FVIII levels on Day 0 were eliminated for all participants.
2.2.4 & 2.2.5	Added Summary of Non-clinical Experience with [REDACTED]	The preclinical study results provide evidence to support the design of cohort.
2.2.5	Added preclinical experience with [REDACTED]	The preclinical study results provide evidence to support the design of cohort 1.
2.3.1	Added risks associated with [REDACTED]	The risks associated with [REDACTED] were provided to support the design of cohort 2.
2.3.1	Added risks associated with [REDACTED]	The risks associated with [REDACTED] were provided to support the design of cohort 1
2.4	Updated Study Rationale with most recent published data.	Results from gene therapy in hemophilia have been published since the previous amendment. Data from the Spark participants to date provides the rationale for this amendment.
4.1.1	Added cohorts 1 and 2 to the study design and provided instruction on sequence of enrollment.	Details for the expansion and enrollment sequence of the two cohorts are included. A description of the expansion of cohorts up to

		10 participants is described if additional data is needed.
4.1.1	Refined dose cohort expansion.	Details for the expansion and enrollment sequence of the 3 doses into two cohorts are included. A description of the expansion of cohorts up to 10 participants is described if additional data is needed.
4.1.3.1	Added SARS-coV2 testing	Multiple effects of COVID-19 on the hemostatic system have been described, including the development of anti-phospholipid antibodies (Lupus-like anticoagulants), which might confound interpretation of one-stage clotting factor VIII assays
4.2.2	Updated study design to include up to 40 participants.	The addition of one additional dose and expansion of all dose levels into two cohorts will require an increase in the number of participants in the trial.
5.2	Provided clarification in eligibility for assessing liver fibrosis.	On occasion, discordant results as it relates to liver health have been found in review of the medical record. The Fibro scan is considered the gold standard in determining liver elasticity/fibrosis. This protocol was clarified to elevate this test as the determinant for eligibility.
5.2	Exclusion criteria updated to included gastrointestinal disease, cancer, and latent infectious disease due to the addition of immunomodulation in the amendment.	The use of immunomodulation agents has been included in the study design. The exclusion criteria changes are reflective of contraindications identified in the package insert for ██████
6.2.6	Added ability to perform genetic analyses on archived samples	Archived samples may be used for genetic sequencing if the participant provides consent.
6.4.1	Changed the FVIII PK analysis from Day 0 to historic or during the screening period.	The PK analysis added to the complexity of Day 0. Historic PK results provide sufficient information should it be needed to compare FVIII response post gene therapy.

6.7.1	Changed the Day 0 FVIII infusion to a routine prophylactic treatment.	The PK analysis is no longer needed on Day 0. Patients with hemophilia administer prophylactic treatments routinely. This will provide bleed protection for a portion of week one.
6.5 & 6.6	Added additional laboratory assessments for Cohort 2 prior to dosing day and following vector infusion.	Additional laboratory assessments are required for participants in cohort 2 due to the planned use of ██████. The testing three to seven days prior to dosing day is required to confirm that the critical laboratory values have not changed during the screening period. Weekly follow up while on immunomodulation is recommended in the clinical management of participants receiving immunomodulation. NAAT testing for infection with SARS-coV2 in asymptomatic study participants prior to immune suppression and to recommend NAAT testing in symptomatic study participants prior to immune suppression has been included for participant safety.
7	Added information on description, storage, preparation, handling, disposal, accountability, and labeling of Sponsor-provided immunomodulators	Language was added to support Sponsor supply of immunomodulators.
9.1.1	Updated AE language	AE language was updated to include standard toxicology reporting. Clarification of the timeframe to collect AEs was provided.
11.1.9	Added requirements for eCRF data to be locked before a site is closed.	Clarification was provided to ensure eCRF data for a site is locked prior to that site being closed.
Throughout	Updated text and references as they relate to the Immunomodulatory clinical experience and the cohort design in this trial.	Literature in the gene therapy is regularly published. Data and references were updated in all areas of the protocol to maintain relevant resources. Data from the

		Spark participants to date provides the rationale for this amendment.
--	--	---

Document	Description of Main Changes
Amendment 1	
 1. Incorporated minor edits for readability, corrected formatting issues, and corrected typographical errors to improve accuracy and clarity and updated abbreviations, citations and references. Changes and updates from the Sponsor’s latest protocol template were incorporated. 2. Updated study schematic figure 1. 3. Removed language requiring prophylactic steroid administration on Week 4. 4. ██████████ corticosteroids in response to an immune response trigger. 5. Updated language to allow the Investigator in collaboration with the Sponsor to use other immunomodulatory agents, should they be required, to reduce long term and high dose steroid exposure 6. Inserted Thiopurine methyltransferase (TPMT) as a screening requirement. 7. Added risks associated with ██████████. 8. Updated text and references as it relates to immunomodulatory clinical experience in Hemophilia Gene Therapy trials.

LDH	Lactate dehydrogenase
mITT	Modified Intention to Treat
PBMC	Peripheral blood mononuclear cells
PK	Pharmacokinetics
RBC	Red blood cell
SAE	Serious treatment-emergent adverse event
SD	Standard deviation
SOC	System organ class

SPK-8016	Study drug in this protocol  
TEAE	Treatment-emergent adverse event
WBC	White blood cell

1. INTRODUCTION

SPK-8016 is an investigational adeno-associated virus (AAV) gene therapy medicinal product. SPK-8016 was being developed by Spark Therapeutics for the treatment of hemophilia A, a deficiency of blood coagulation factor VIII (FVIII) that is an inherited X-linked recessive mutation carried by females and expressed mainly by males, affecting approximately 1 in 4,000 male births. The severity of hemophilia A is characterized by the endogenous level of FVIII measured in plasma.

This document describes the analyses that support the aCSR for study SPK-8016-101 based on protocol SPK-8016-101 Amendment 2, Version 3.0 dated 09-Feb-2021.

1.1. STUDY OBJECTIVES REPORTED IN THE aCSR

1.1.1. PRIMARY OBJECTIVES REPORTED IN THE aCSR

- To evaluate the safety and tolerability of SPK-8016.
- To evaluate the efficacy as evidenced by prevention of bleeds and level of FVIII expression with SPK-8016.

1.1.2. SECONDARY OBJECTIVES REPORTED IN THE aCSR

- To evaluate additional parameters associated with SPK-8016 directed FVIII expression.
- To characterize the immune response to the transgene product.

1.2. ENDPOINTS REPORTED IN THE aCSR

1.2.1. EFFICACY ENDPOINTS

- Annualized bleeding rate (ABR) post-SPK-8016 infusion
- Annualized FVIII infusion rate (AIR) post-SPK-8016 infusion

1.2.2. PHARMACOKINETICS ENDPOINTS

- Peak FVIII activity
- Median FVIII activity from weeks 40 through 52 post-SPK-8016 infusion

1.2.3. SAFETY ENDPOINTS

For safety and tolerability:

- Exposure of immunomodulatory treatment
- Adverse events (SPK-8016 related and immunomodulation-related)
- Clinical laboratory evaluation

1.3. STUDY DESIGN

This is a Phase 1/2a, open-label, non-randomized, dose escalation study to evaluate the safety, tolerability, and efficacy of a single IV infusion of SPK-8016 in men with clinically severe hemophilia A, and no measurable inhibitor against FVIII.

1.3.1. STATISTICAL HYPOTHESES

No statistical hypotheses will be tested as part of this protocol. This study will be used to establish an initial safety and efficacy profile of SPK-8016.

2. ANALYSIS POPULATIONS

The Full Analysis Set (FAS) is defined as all participants who receive the infusion of SPK-8016. The analyses of the described endpoints will be performed in this population.

3. STATISTICAL ANALYSES SUPPORTING THE aCSR

3.1. GENERAL CONSIDERATIONS

Unless otherwise specified, continuous variables will be summarized by the following descriptive statistics: number of observations, mean, median, standard deviation, minimum, and maximum. Categorical variables will be presented with the number and percentage in each category.

3.2. ANALYSIS OF EFFICACY

3.2.1. ANNUALIZED BLEEDING RATE (ABR)

ABR following SPK-8016 administration and beginning 28 days following SPK-8016 administration will be listed by participant. Bleeds will be categorized and analyzed using the following definitions:

Bleed Type	Description
All Bleeds	This will be comprised of both treated and non-treated bleeds, except when the bleed is a result of a surgery or procedure, including cosmetic (ie. Tattoos) or dental procedures.
Treated Bleeds	A bleed is considered to be a “treated bleed” if it is reported on the eCRF as being treated with Factor VIII and is not a result of a surgery or procedure. This category will only be summarized for bleeding events post-SPK-8016 administration, due to the limitation of baseline bleeding rates.
Spontaneous Bleeds	A bleed is considered to be a “spontaneous bleed” if it is reported on the eCRF as being spontaneous.
All Joint Bleeds	This will be comprised of both treated and non-treated bleeds in a joint as specified in the eCRF and not a result of a surgery or procedure. This category will only be summarized for bleeding events post-SPK-8011 administration, due to the limitation of baseline bleeding rates.

ABR Calculation Rules:

3 Day Rule: Two or more bleeds of the same type (e.g., “joint,” “muscle,” or “other”) and at the same anatomical location are considered one bleed if the second occurs within 72 hours from the last treatment for the first bleed. The last treatment is defined as the last treatment before a new bleed occurs, either in the same or in a different location.

Censoring Rule: If a participant loses transgene derived FVIII, the duration of follow-up time for calculation of ABR will be censored on the day in which the central lab one-stage FVIII activity level falls to equal or below diagnostic historical value 28 days or later following SPK-8016 infusion. FVIII activity level equal or below diagnostic historical value is considered as complete loss of expression.

ABR Calculation Formula:

ABR post 28 days will be computed as:

$$ABR_{28} = \frac{365.25 * \text{observed number of bleeding events}}{EFF\ FUP\ (in\ days) - 28}$$

rounded to the tenth place.

ABR post day 0 will be computed as:

$$ABR = \frac{365.25 * \text{observed number of bleeding events}}{EFF\ FUP\ (in\ days)}$$

rounded to the tenth place. EFF FUP, the duration of efficacy follow-up.

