2.1.3.2 Current Prevention

Chronic arthropathy is the major morbidity of hemophilia resulting from recurrent spontaneous bleeds into the joints. Many studies have shown that, even at high doses, on-demand therapy is not effective in preventing arthropathy (Petrini, 1991; Aledort, 1994). Thus, scheduled protein replacement to prevent bleeding (prophylactic treatment) as the standard of care for hemophilia rather than on-demand treatment was facilitated by the introduction of rFVIII concentrates in the early 1990's. Prophylactic treatment (regular IV infusions ranging from twice a week up to every other day) aims to maintain plasma FVIII levels $\geq 1\%$, thereby changing the expected phenotype from severe to moderate hemophilia (Nilsson, 1992). Observations of individuals with moderate hemophilia, and a generation of clinical research in hemophilia patients treated prophylactically with clotting factor replacement, have documented that minimal elevations in the levels of normal circulating clotting factor activity $\geq 1\%$ are sufficient to prevent bleeding, and this has been demonstrated in the Swedish prophylactic studies (summarized in Löfqvist, 1997; Ljung, 1998; and Nilsson, 1992).

Prophylactic therapy, which aims to convert the severe phenotype to moderate through regular infusions of clotting factor, with 100% adherence to dosing regimen, is more effective than on-demand treatment at preserving joint health (Manco-Johnson 2007; Gringeri, 2011). It has revolutionized health outcomes in hemophilia by enabling affected individuals to participate in physical activities (Wang, 2016; Negrier, 2013), and natural history data suggests that FVIII:C around 12% of normal levels may be sufficient to protect from spontaneous joint bleeds (Mahdi, 2015; den Uijl, 2011). However, regular replacement therapy poses significant challenges for the hemophilia community, including the frequency of IV infusions required, necessity to adhere rigorously to the prophylactic regimen, variability in individual pharmacokinetics (PK) requiring personalized regimens, potential development of neutralizing alloantibodies ("inhibitors"), and cost-effectiveness.

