3.3 Primary Endpoints

The primary endpoints include the following:

- For safety and tolerability:
 - Incidence of adverse events, including clinically significant abnormal laboratory values.
 - Occurrence of hepatic transaminase elevation requiring immunosuppression.
- For efficacy:
 - Peak and steady-state FVIII activity levels assessed by coagulation clotting assays. In this study, steady-state levels are based on FVIII:C measurements starting 12 weeks post vector administration and without the use of exogenous FVIII products since vector administration.
 - Number of bleeding events (spontaneous and traumatic) since vector administration.
 - Number of FVIII infusions since vector administration.

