ALT levels and extinguished the ELISpot signal in all cases. Two of the 5 participants who received corticosteroids in the 2×10^{12} vg/kg dose group, however, showed loss of transgene expression likely due to the immune response. Both of these individuals eventually returned to hemophilia prophylaxis regimens, one with recombinant FVIII, the other with emicizumab. Given that 5 of 7 participants in the 2×10^{12} vg/kg group required corticosteroids, including 2 participants who lost FVIII expression, the institution of a consistent, standardized short course of prophylactic corticosteroids appeared warranted in an attempt to pre-emptively manage potential immune responses. In the first 2 participants administered SPK-8011 at 2×10^{12} vg/kg using prophylactic oral corticosteroids (1 mg/kg or 60-80 mg), the first was started on corticosteroids on Day 27 due to falling FVIII and the second was started on Day 26 due to rising ALT and decreasing FVIII expression. In both of these participants, early initiation of corticosteroids resulted in a transient supraphysiologic increase in FVIII levels to greater than 200%. An intermediate dose cohort (1.5×10^{12} vg/kg) was initiated. Reduction of the vector genome dose was successful in terms of avoiding supraphysiologic levels of FVIII upon initiation of corticosteroids, but in all participants where corticosteroids have been started prior to 6 weeks post vector infusion, tapering off has been challenging, and consequently, prolonged courses have been required, with associated steroid related side effects. [REDACTED]

[REDACTED] Because of the prolonged steroid taper when steroids were administered beginning at 4 weeks, which was not observed with later initiation of steroids, prophylactic steroids will be avoided going forward.

Based on discussions with expert immunology consultants, the Sponsor proposes to again investigate administration of steroids only in response to one of the previously described triggers, i.e., declining FVIII levels or rising transaminases, [REDACTED]

[REDACTED] Oral corticosteroids may be utilized, if clinically indicated. ELISpot is an exploratory assay and not predictive as a trigger for immunomodulation.

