10.5.2 Efficacy Analysis

Summary statistics will be created by SPK-8016 dose group for the following parameters:

- Peak and steady-state FVIII activity levels assessed by coagulation clotting assays. In this study, steady-state levels are based on FVIII:C measurements starting 12 weeks post vector administration and without the use of exogenous FVIII products since vector administration. See Section 10.5.3 for additional details.
- The number of bleeding events expressed as the ABR per participant (spontaneous and traumatic combined) following SPK-8016 administration and beginning 28 days following SPK-8016 administration.
- Absolute change in ABR for all bleeding events and for bleeding events observed beginning 28 days following SPK-8016 administration from the hemophilia history-based ABR for the 52 weeks prior to SPK-8016 administration.
- Proportion of participants with a post SPK-8016 administration ABR of 0 or 1 (separately for all bleeding events and for bleeding events reported beginning at least 28 days following SPK-8016 administration).
- Number of recorded FVIII infusions per participant (referred to in the protocol as annualized FVIII usage) following SPK-8016 administration and beginning 28 days following SPK-8016 administration.
- Absolute change in the number of recorded FVIII infusions following SPK-8016 administration (all infusions and infusions reported beginning 28 days following SPK-8016 administration) from the prior 52-week hemophilia history.

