3.2.2. ANNUALIZED INFUSION RATE (AIR)

AIR following SPK-8016 administration and beginning 28 days following SPK-8016 administration will be listed by participant. Two main types of infusions were reported: “all infusions” and “infusions to treat bleeds”. The number of recorded FVIII infusion events will be categorized and analyzed using these two main categories of infusions. The reported infusions during the prior 52-week hemophilia history were “all infusions” only.

AIR Calculation Rules:

Censoring Rule: If a participant loses transgene derived FVIII, the duration of follow-up time for calculation of AIR will be censored on the day in which the central lab one-stage FVIII activity level falls to equal or below diagnostic historical value 28 days or later following SPK-8016 infusion.

AIR Calculation Formula:

AIR post 28 days will be calculated as follows:

$$AIR_{28} = \frac{365.25 * \text{observed number of FVIII infusions}}{EFF\ FUP\ (in\ days) - 28}$$

rounded to the nearest integer.

AIR post day0 will be calculated as follows:

$$AIR = \frac{365.25 * \text{observed number of FVIII infusions}}{EFF\ FUP\ (in\ days)}$$

rounded to the nearest integer. EFF FUP, the duration of efficacy follow-up.

Change in AIR and AIR28 will only be calculated for the number of recorded “all infusions” because only all infusions are collected for the prior to gene therapy period.

Change in AIR will be calculated as:

$$\text{Change in AIR} = \text{Post Infusion AIR} - \text{Baseline AIR}$$

Change in AIR28 will be calculated as:

$$\text{Change in AIR28} = \text{Post Infusion AIR28} - \text{Baseline AIR}$$

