3.8. PARTICIPANT DISPOSITION

The number of participants screened and the number of participants not eligible for the study (overall and categorized by reason: consent withdrawal, screen-failure, screened but not enrolled and other) will be presented. Safety and efficacy follow-up time will be calculated for each participant.

Safety follow-up time in days will be calculated as:

$$\text{SAF FUP} = (\text{lesser of date of study withdrawal or date of last contact}) - \text{SPK-8016 infusion date} + 1$$

Efficacy follow-up time in days will be calculated as:

$$\text{EFF FUP} = (\text{lesser of date of study withdrawal, date of last contact or date of efficacy censoring}) - \text{SPK-8016 infusion date} + 1$$

Follow-up time will also be displayed in weeks by dividing the days of follow-up by 7 and summarized.

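### The SAP stops counting bleeds and FVIII infusions at complete loss of expression, and its visible text plans no rate over all follow-up, although the protocol's primary endpoints run from vector infusion with no such stop

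*SAP*

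**What the plan says.** Protocol 3.3 lists two event-based primary efficacy endpoints: "Number of bleeding events (spontaneous and traumatic) since vector administration" and "Number of FVIII infusions since vector administration". Protocol 10.5.2 annualizes the bleeds per participant and also plans "Number of recorded FVIII infusions per participant (referred to in the protocol as annualized FVIII usage) following SPK-8016 administration", each from infusion and again from Day 28. Protocol 10.3 places the efficacy analyses in all infused participants. None of these sections stops the count when expression is lost.

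The SAP keeps the population (section 2) and describes both rates as post-infusion (1.2.1), but it adds a censoring rule. For ABR, section 3.2.1 states: "If a participant loses transgene derived FVIII, the duration of follow-up time for calculation of ABR will be censored on the day in which". The condition that follows is a one-stage FVIII result from the central laboratory at or below the historical diagnostic value, from Day 28 on; the SAP calls this complete loss. Section 3.2.2 repeats the rule for infusions: "the duration of follow-up time for calculation of AIR will be censored on the day in which the central lab one-stage FVIII activity level" meets the same condition. Section 3.8 carries it into the efficacy follow-up time (EFF FUP), which runs to the "lesser of date of study withdrawal, date of last contact or date of efficacy censoring".

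EFF FUP is the denominator of ABR and AIR, and EFF FUP minus 28 is the denominator of ABR28 and AIR28. Both change-in-AIR measures inherit it. Section 3.8 also defines an uncensored safety follow-up time (SAF FUP), which enters no rate. The list of tables and listings is in an appendix that is not available here.

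**The concern.** Three problems follow from the rule.

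1. **Censoring depends on the outcome.** Follow-up stops because the vector has failed, so the rates no longer describe all follow-up in all infused participants. Change in AIR becomes lopsided: its baseline is a full prior 52 weeks of all infusions, while the post-infusion rate leaves out prophylaxis given after failure.
2. **Only time is censored.** The numerator is the observed number of events, with no stated cut-off. Dropping later events is the natural reading. Keeping them over the shortened time would give the opposite result.
3. **The trigger does not exclude samples taken after infused FVIII.** Protocol 2.1.3.2 says prophylaxis "aims to maintain plasma FVIII levels" of at least 1%, while inclusion criterion 3a is a level below 1%. A 3a participant who resumes prophylaxis before reaching the threshold may never be censored. The protocol's own steady-state definition (3.3) does exclude exogenous FVIII.

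At stake is whether a participant who fails completely and goes back to FVIII prophylaxis can show the same AIR as a durable responder. The event is foreseeable. Protocol 2.4 reports that in the sponsor's similar SPK-8011 trial, 2 of 9 participants at 2×10¹² vg/kg lost expression and returned to prophylaxis. Protocol 4.1.3 adds: "Both of these individuals eventually returned to hemophilia prophylaxis regimens, one with recombinant FVIII, the other with emicizumab".

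**Working it through.** The study is descriptive, so there is no power or alpha figure to reproduce. The check applies the SAP's own formulas to assumed courses, once with EFF FUP cut at loss and once over all follow-up.

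**Inputs from the documents**
- Rates (SAP 3.2.1, 3.2.2): 365.25 × events / EFF FUP; for the 28-day versions, 365.25 × events / (EFF FUP − 28).
- EFF FUP = end date − infusion date + 1 (SAP 3.8).
- Prophylaxis at 2 to 3.5 infusions a week (Protocol 2.1.3.2).
- FVIII prophylaxis allowed in the first 14 days if medically necessary (Protocol 7.9.2), and later if clinically indicated (7.9.3).

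**Assumptions:** the day of loss, the bleed counts, prophylaxis starting immediately at loss, and 52 weeks of follow-up. AIR is for the all-infusions category.

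**AIR, loss at week 16**
- EFF FUP at week 52: 364 + 1 = 365. At loss: 112 + 1 = 113.
- Infusions after loss: 36 weeks × 2 = 72, or × 3.5 = 126.
- All follow-up: 365.25 × 72/365 = 72.0; 365.25 × 126/365 = 126.1.
- Later infusions kept over the shortened time: 365.25 × 72/113 = 232.7; 365.25 × 126/113 = 407.3.
- With two weeks of early prophylaxis (4 to 7 infusions), censored: 365.25 × 4/113 = 12.9; 365.25 × 7/113 = 22.6. All follow-up: 365.25 × 76/365 = 76.1; 365.25 × 133/365 = 133.1.
- Prophylaxis resumed at week 15, before the threshold, and never censored: 37 weeks give 74 to 129.5 infusions, so AIR is 74.1 to 129.6.

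| Course | AIR, events and time both cut at loss | AIR, all follow-up |
|---|---|---|
| Loss at week 16, no earlier infusions | 0 | 72–126 |
| Same, with 14 days of early prophylaxis | 13–23 | 76–133 |
| Prophylaxis resumed at week 15, trigger never met | 74–130 (not censored) | 74–130 |

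The first and third rows are nearly the same clinical course, yet the SAP reports 0 for one and 74–130 for the other.

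**Group mean, nine participants.** Suppose two lose expression, one resumes FVIII, one takes emicizumab (no FVIII infusions), and everyone else has AIR 0. The censored mean is 0. Over all follow-up it is 72.0/9 = 8.0 to 126.1/9 = 14.0. If both resumed FVIII it would be 16 to 28. With one FVIII resumer, the result by week of loss is:
- Week 8 (44 weeks, 88 to 154 infusions): 9.8 to 17.1.
- Week 26 (26 weeks, 52 to 91 infusions): 5.8 to 10.1.

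**ABR28, loss at week 12.** EFF FUP is 85, so the censored denominator is 85 − 28 = 57 days; over all follow-up it is 365 − 28 = 337.
- One bleed between Day 28 and loss, none after: 365.25 × 1/57 = 6.4 censored; 365.25 × 1/337 = 1.1 over all follow-up.
- No bleed before loss, four after: 0 censored; 365.25 × 4/337 = 4.3 over all follow-up.

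At the extreme, loss on Day 28 gives EFF FUP 29, so ABR28 is divided by a single day.

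**The case against.** The strongest reply is that a rate while expressing is a legitimate quantity in a descriptive study. After loss, bleeding reflects the resumed therapy rather than the vector, and uncensored AIR does not count emicizumab, so it can also hide failure. This stands as a reason to keep the censored rate and to list the resumed product. It does not justify replacing the protocol's endpoint.

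The protocol fixes a start for the counts but no explicit end or formula, so follow-up to withdrawal or last contact is an inference. It is the ordinary reading of a count from infusion onward with no stated stop, and SAF FUP already has that end point.

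The size is uncertain, and this stands. The day of loss is assumed, and participants may return to prophylaxis later than at once. The 2 of 9 come from a different vector, and the protocol does not say that those two fell to their historical values. Protocol 2.5 reports the four participants already dosed here at around 6% (three) and above 20% (one), so the rule may affect nobody. The visible SAP lists ABR and AIR by participant, so the group mean above only shows scale.

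Much is visible indirectly: FVIII levels are listed, and a gap between SAF FUP and EFF FUP reveals a censored participant. That allows detection but does not give the rate. The unseen table list might contain an uncensored version, but the SAP body gives no formula for one.

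The missing numerator window needs only a wording change, since cutting events with time is the natural reading. The 233–407 result is what happens if the rule is applied literally, not a likely reported value.

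**Conclusion.** The concern holds. Followed as written, the SAP turns two protocol primary endpoints into rates up to complete loss of expression and, in its visible text, provides no rate over all follow-up. For AIR this usually favours SPK-8016; for ABR the direction depends on when bleeds occur relative to loss. The illustrated gap for one affected participant is large, but it rests on the assumed loss date, immediate return to FVIII prophylaxis and the 2 to 3.5 weekly frequency. In groups this small, one such participant can dominate a mean. If no participant meets the trigger, nothing changes. The point should be fixed because the departure from the protocol is unexplained and the correction is cheap.

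**What to change.** - Report ABR, AIR and change in AIR, from infusion and from Day 28, to withdrawal or last contact for every infused participant. The SAF FUP window already supplies the denominator.
- Keep the censored rates as a supportive analysis labelled as covering time while expressing, with events and time cut at the same date.
- State how FVIII samples taken after exogenous FVIII are treated when deciding whether the loss trigger is met.
- List for each participant the date of loss, the date prophylaxis resumed and the product (FVIII or emicizumab).

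The cost is one extra set of derived variables from data already collected. The drawback is that ABR after resumption partly reflects the resumed prophylaxis; the listing and the supportive rates make that visible.
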